12.5.5 Patient reported outcomes

Not applicable

12.7 Interim analyses

There will be informal PK checks (together with a review of efficacy and safety data as available) at various time points, and two planned interim data assessments, one between cohorts 1 and 2, and one again (of both Cohorts' data) after all patients in Cohort 2 have completed Day 43.

After the first 9 patients in Cohort 1 and the first 3 patients in the highest age subgroup of Cohort 2 have completed Day 15, artemether, DHA, and lumefantrine concentrations will be reviewed (together with a review of efficacy and safety data as available) for potential dose modifications (See [Section 6.5.1.2](#)). Another such review will be done after the first 9 patients of Cohort 2 have completed Day 15 (and optionally once 9 patients from the age group 15-28 days have completed Day 15). All available data including PK parameters, safety and efficacy will be reviewed by the DMC at these time points as described in [Figure 3-2](#).

After all patients in Cohort 1 have completed the core period (Day 43), artemether, DHA, and lumefantrine concentrations, PK parameters, key efficacy and safety endpoints will be analyzed by the study biostatistics team (interim assessment 1). These results will be reviewed by the DMC to reach a decision about progression to Cohort 2 and the starting dose level in that Cohort. A second interim assessment will be performed after all patients have completed the core period of the study (Day 43). For the second interim assessment, all data up to Day 43 will be cleaned and included.

Additional interim assessments may be conducted to support decision making based on early read-out of study data.

Additional ad-hoc safety reviews may be requested by the DMC or Novartis if needed (e.g. in case of SAEs).

12.8 Sample size calculation

The sample size is calculated and justified based on the precision of estimating artemether C_{max} (primary endpoint) and Day 8 (168 h) lumefantrine concentration (secondary endpoint) separately for Cohort 1 and Cohort 2.

12.8.1 Primary endpoint(s)

Artemether C_{max} (represents the higher concentration between the concentrations at 1 hour and 2 hours) after the first dose is the primary endpoint. The distribution of C_{max} is best described by log normal distribution. The half width of the 2-sided 90% confidence interval for log C_{max} is the target for sample size calculation. The relevant historical data for sample size calculation are the standard deviations of log C_{max} , which are usually invariant to the dosage (See [Table 12-1](#)).

Table 12-1 Standard deviation for log C_{max} in Coartem studies A2102 and B2306

| Study and formulation of artemether-lumefantrine | Artemether C _{max} | Day 8 Lumefantrine concentration |
|--|-----------------------------|----------------------------------|
| A2102* (healthy volunteers) 80:480 mg tablet | 0.58 | - |
| A2102 (healthy volunteers) 4 tablets of 20:120 mg | 0.52 | - |
| B2306 (infants >28 days of age) 20:120 mg dispersible tablet | 0.65 | 0.654 |

*Study CCOA566A2102; **Study CCOA566B2306

The table shows that the standard deviation for log C_{max} was about 12% to 25% higher for infants in Study B2306 than for healthy volunteers in Study A2102. The patient population in the current study (B2307) is similar to the patient population in Study B2306.

For log C_{max}, a standard deviation of 0.65 from Study B2306 will therefore be used. Based on the standard deviation of 0.65 in log scale, a sample size of 16 evaluable patients will provide 80% probability that the observed half width of 2-sided 90% CI for log C_{max} is ≤ 0.337 or 1.4 times (covering the targeted C_{max}) in terms of ratio (nQuery Advisor 8). This sample size is applied to each cohort.

PK sampling will be designed in order to get all patients evaluable for artemether C_{max} analysis. Taking into account about 10% of patients not evaluable for this PK analysis, about 18 patients should be enrolled in each cohort.

For each cohort the sample size will be increased slightly to allow for higher dropouts for the secondary endpoint, Day 8 (168 h) lumefantrine concentration (see [Section 12.8.2](#)).

12.8.2 Secondary endpoint(s)

Power consideration for Day 8 (168 h) lumefantrine concentration

The Day 8 (168 h) lumefantrine concentration is the key secondary endpoint. The distribution of Day 8 lumefantrine concentration is best described by log normal distribution. In Study B2306, the standard deviation for the log concentration from 16 infants was 0.65. Based on the standard deviation of 0.65 in log scale, a sample size of 16 evaluable patients will provide 80% probability that the observed half width of 2-sided 90% CI for the log concentration is ≤ 0.337 or 1.4 times in terms of ratio (nQuery Advisor 8). This sample size is applied to each cohort.

The percentage of patients who are not evaluable for Day 8 lumefantrine concentration may be higher than that for artemether C_{max} which is based on the concentrations on Day 1. Taking into account about 25% of patients not evaluable for this PK analysis, about 22 patients will be enrolled in each cohort in order to achieve the number of patients evaluable for this analysis as specified above.

Power consideration for PK checking in each cohort

After about 9 patients have been enrolled in each cohort, PK checking will be performed to see if the dose level should be adjusted. Considering that about 10% of patients would be non-evaluable for artemether C_{max}, this will lead to about 8 patients evaluable for artemether C_{max}.

The probability that the observed half width of 2-sided 90% CI in log scale is ≤ 0.693 or 2 in terms of ratio for artemether C_{max} is 96% if the standard deviation in log scale is same as the assumed 0.65 or 80% if the standard deviation in log scale is as high as 0.85 (nQuery Advisor 8).

Note:

The requirement for an evaluable number of patients is 16 for both the primary endpoint (artemether C_{max} (max concentration between concentrations at 1 hour and 2 hours)) and the secondary endpoint (Day 8 (168 h) lumefantrine concentration). An additional number of patients is included due to potential dropouts for each endpoint. In case that the number of dropouts is less than expected, the enrollment for a cohort may be stopped after at least 16 patients are deemed evaluable for PK analyses (C_{max} or Day 8 concentration).

In order to support an early readout of the study based on observed PK, efficacy and safety, enrollment may be stopped. Thereafter, the criterion of 0.337 for the observed half width of 2-sided 90% CI for the log concentration will be increased to a threshold that is appropriate for the sample size.

Additional modeling and simulation may be performed to support the planned analyses.

13 Ethical considerations and administrative procedures

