3.1.2 Secondary endpoint(s)

Power consideration for Day 8 (168 h) lumefantrine concentration

The Day 8 (168 h) lumefantrine concentration is the key secondary endpoint. The distribution of Day 8 lumefantrine concentration is best described by log normal distribution. In Study B2306, the standard deviation for the log concentration from 16 infants was 0.65. Based on the standard deviation of 0.65 in log scale, a sample size of 16 evaluable patients will provide 80% probability that the observed half width of 2-sided 90% CI for the log concentration is ≤ 0.337 or 1.4 times in terms of ratio (nQuery Advisor 8). This sample size is applied to each cohort.

The percentage of patients who are not evaluable for Day 8 lumefantrine concentration may be higher than that for artemether C_{max} which is based on the concentrations on Day 1. Taking into account about 25% of patients not evaluable for this PK analysis, about 22 patients will be enrolled in each cohort in order to achieve the number of patients evaluable for this analysis as specified above.

Power consideration for PK checking in each cohort

After about 9 patients have been enrolled in each cohort, PK checking will be performed to see if the dose level should be adjusted. Considering that about 10% of patients would be non-evaluable for artemether C_{max} , this will lead to about 8 patients evaluable for artemether C_{max} . The probability that the observed half width of 2-sided 90% CI in log scale is ≤ 0.693 or 2 in terms of ratio for artemether C_{max} is 96% if the standard deviation in log scale is same as the assumed 0.65 or 80% if the standard deviation in log scale is as high as 0.85 (nQuery Advisor 8). Additional optional PK checks can also be implemented.

Note:

The requirement for an evaluable number of patients is 16 for both the primary endpoint (artemether C_{max} (max concentration between concentrations at 1 hour and 2 hours)) and the secondary endpoint (Day 8 (168 h) lumefantrine concentration). An additional number of patients is included due to potential dropouts for each endpoint. In case that the number of dropouts is less than expected, the enrollment for a cohort may be stopped after at least 16 patients are deemed evaluable for PK analyses (C_{max} or Day 8 concentration).

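### The 96% precision probability quoted for the 9-patient PK check computes to about 98.5–99%, and it does not fit the 80% paired with it

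*Protocol*

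**What the plan says.** Protocol 12.8.2, under the heading on PK checking in each cohort, plans a check after about 9 patients. It allows for loss ("Considering that about 10% of patients would be non-evaluable") and concludes that "this will lead to about 8 patients evaluable for artemether" Cmax. The precision criterion is that the "observed half width of 2-sided 90% CI in log scale is ≤ 0.693 or 2 in terms of ratio". The probability of meeting it is given as "96% if the standard deviation in log scale is same as the assumed 0.65 or 80% if the standard deviation in log scale" rises to 0.85, and nQuery Advisor 8 is cited. SAP 3.1.2 carries the same statement ("is 96% if the standard deviation in log scale is same as the assumed 0.65").

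The main sample-size statement has the same form. In Protocol 12.8.1, "a sample size of 16 evaluable patients will provide 80% probability" of a half-width no greater than 0.337 with SD 0.65. Protocol 12.8.2 and SAP 3.1.1 and 3.1.2 repeat it.

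Neither document says whether the probabilities are unconditional or conditional on the interval covering the true mean.

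**The concern.** The two PK-check probabilities share the same number of patients, confidence level and half-width; only the SD differs. Once the formula is chosen, one figure fixes the other, so a reader should be able to reproduce both from the sentence itself. That fails for the 96%, and the two figures do not fit together.

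This sentence is the only quantified support for the size of the 9-patient check, and that check informs whether the dose level is changed for later patients. A stated operating characteristic that cannot be reproduced invites questions about the rest of the section, even when the error is small and in the safe direction.

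**Working it through.** **Inputs**

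- Evaluable patients at the check: 9 × 0.90 = 8.1, taken as 8 (Protocol 12.8.2).
- Half-width limit w = 0.693, which is ln 2; 2-sided 90% interval (Protocol 12.8.2).
- Log-scale SD: 0.65 or 0.85 (Protocol 12.8.2).
- Interval: Student t on log data with n − 1 degrees of freedom (SAP 5.7.1).

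**Formulas**

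The half-width is t(0.95, n−1) × s/√n. It is at most w when s ≤ w√n/t.

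- *Unconditional:* P = Pr{χ² with n−1 df ≤ (n−1) n w² / (t² SD²)}.
- *Conditional on coverage:* the same event, given that the interval contains the true mean. This weights the density of s by 2Φ(t s/SD) − 1, integrates up to w√n/t and divides by 0.90.

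**PK check, n = 8**

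t(0.95, 7) = 1.8946, so s must not exceed 0.693 × 2.8284/1.8946 = 1.0346.

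- SD 0.65: 7 × (1.0346/0.65)² = 17.73, and Pr(χ²₇ ≤ 17.73) = 98.7%.
- SD 0.85: 7 × (1.0346/0.85)² = 10.37, and Pr(χ²₇ ≤ 10.37) = 83.1%.

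| SD | Stated | Unconditional | Conditional |
|---|---|---|---|
| 0.65 | 96% | 98.7% | 98.5% |
| 0.85 | 80% | 83.1% | 81.5% |

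Simulation with 400,000 replicates agrees: 98.7% and 98.5% at SD 0.65, 83.2% and 81.5% at SD 0.85.

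**Can another reading give 96%?** At n = 8 and SD 0.65, the joint probability of meeting the width and covering the mean is 88.7%. A normal quantile in place of t gives 99.9%, and a 95% interval gives 87.7%. None is 96%.

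**Can another n give both figures?** (unconditional, with conditional in brackets)

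| n | SD 0.65 | SD 0.85 |
|---|---|---|
| 7 | 95.1% (94.6%) | 71.4% (68.7%) |
| 8 | 98.7% (98.5%) | 83.1% (81.5%) |
| 9 | 99.7% (99.7%) | 91.4% (90.5%) |

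No row gives 96% and 80% together. Put the other way, at n = 8 the two stated probabilities correspond to SDs of 0.714 and 0.874 unconditionally (0.707 and 0.861 conditionally), not 0.65 and 0.85.

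**The figure for 16 patients, for comparison**

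With w = 0.337 and SD 0.65, n = 15 gives 80.2% unconditionally and 78.6% conditionally; n = 16 gives 86.3% and 85.2%. Sixteen is the smallest n that reaches 80% under the conditional formula. Under the unconditional formula it is 15.

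**The case against.** The strongest defence is that these are planning figures. The evaluable number is only approximate, 0.85 is a round stress value, and the software may have used the coverage-conditional formula. Much of this stands:

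- **The 80% at SD 0.85** lies 1.5 points below the conditional value of 81.5%. Taken alone, it could pass as rounding under an unnamed variant.
- **The 80% at 16 patients** is a target. The half-widths are round ratios, 1.4 and 2, chosen first, and n was then found. Sixteen patients do reach 80%.
- **Direction and consequence.** Computed precision is better than stated throughout. Protocol 3 and 12.5.3 rest the check on whether Cmax lies within approximately 2-fold of earlier values, with other PK, safety and efficacy data. No half-width probability enters that decision.

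The defence does not rescue the 96%. The conditional formula gives 98.5%, and moving to 7 patients to approach 96% takes the other figure down to about 70%.

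A reader might infer more: that all three stated probabilities are wrong, or that the sample size is unsound. The first two bullets rule out the former, and the direction of the error rules out the latter. A reader might also link the error to the early-readout rule, under which the 0.337 criterion "will be increased to a threshold that is appropriate for the sample size". The documents tie that threshold to no probability and no sample size. How it would be set is a separate missing detail and adds no weight here.

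**Conclusion.** The 96% in Protocol 12.8.2 and SAP 3.1.2 is wrong as written. From the plan's own inputs it is 98.7%, or 98.5% conditional on coverage, so it is understated by 2.5 to 2.7 points. It is also incompatible with the 80% beside it, which is 3.1 points below the unconditional value and 1.5 below the conditional one.

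This rests on 8 evaluable patients, log-normal Cmax and the SAP's t-interval. It does not depend on which formula the software used, because the 96% fails under both. That the conditional formula was used is only a possibility; the documents do not say.

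The point is minor. The error is conservative, and the 9-patient check, the 16 evaluable and the roughly 22 enrolled per cohort are unaffected.

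**What to change.** In Protocol 12.8.2 and SAP 3.1.2, restate the PK-check pair from one named formula: either 99% and 83% (unconditional) or 98.5% and 81.5% (conditional on the interval covering the true mean). Check the nQuery output to see which variant was run.

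Optionally, describe the figure for 16 patients as at least 80% in Protocol 12.8.1 and 12.8.2 and SAP 3.1.1 and 3.1.2, with the achieved value of 86.3% (85.2% conditional).

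The cost is a text correction. No sample size, analysis or decision rule changes.

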13.1 Regulatory and ethical compliance

This clinical study was designed and shall be implemented, executed and reported in accordance with the International Conference on Harmonisation (ICH) Harmonized Tripartite Guidelines for Good Clinical Practice, with applicable local regulations (including European Directive 2001/20/EC, US CFR 21), and with the ethical principles laid down in the Declaration of Helsinki.

13.2 Responsibilities of the investigator and IRB/IEC

Before initiating a trial, the investigator/institution must obtain approval/favorable opinion from the Institutional Review Board/Independent Ethics Committee (IRB/IEC) for the trial protocol, written informed consent form, consent form updates, subject recruitment procedures (e.g. advertisements) and any other written information to be provided to subjects' parents/legal guardians. Prior to study start, the investigator is required to sign a protocol signature page confirming his/her agreement to conduct the study in accordance with these documents and all of the instructions and procedures found in this protocol and to give access to all relevant data and records to Novartis monitors, auditors, Novartis Quality Assurance representatives, designated agents of Novartis, IRBs/IECs, and regulatory authorities as required. If an inspection of the clinical site is requested by a regulatory authority, the investigator must inform Novartis immediately that this request has been made.

13.3 Publication of study protocol and results

The protocol will be registered in a publicly accessible database such as clinicaltrials.gov and as required in EudraCT. In addition, after study completion (defined as last patient last visit) and finalization of the study report the results of this trial will be submitted for publication and posted in a publicly accessible database of clinical trial results, such as the Novartis clinical trial results website and all required Health Authority websites (e.g. ClinicalTrials.gov, EudraCT etc.).

For details on the Novartis publication policy including authorship criteria, please refer to the Novartis publication policy training materials that were provided to you at the trial investigator meetings.

13.4 Quality Control and Quality Assurance

Novartis maintains a robust Quality Management System (QMS) that includes all activities involved in quality assurance and quality control, to ensure compliance with written Standard Operating Procedures as well as applicable global/local GCP regulations and ICH Guidelines.

Audits of investigator sites, vendors, and Novartis systems are performed by auditors, independent from those involved in conducting, monitoring or performing quality control of the clinical trial. The clinical audit process uses a knowledge/risk based approach.

Audits are conducted to assess GCP compliance with global and local regulatory requirements, protocols and internal SOPs, and are performed according to written Novartisprocesses

14 Protocol adherence

This protocol defines the study objectives, the study procedures and the data to be collected on study participants. Additional assessments required to ensure safety of subjects should be administered as deemed necessary on a case by case basis. Under no circumstances including incidental collection is an investigator allowed to collect additional data or conduct any additional procedures for any purpose involving any investigational drugs under the protocol, other than the purpose of the study. If despite this interdiction prohibition, data, information, observation would be incidentally collected, the investigator shall immediately disclose it to Novartis and not use it for any purpose other than the study, except for the appropriate monitoring on study participants.

Investigators ascertain they will apply due diligence to avoid protocol deviations. If an investigator feels a protocol deviation would improve the conduct of the study this must be considered a protocol amendment, and unless such an amendment is agreed upon by Novartis and approved by the IRB/IEC and Health Authorities, where required, it cannot be implemented.

* In sleep, infant heart rates may drop significantly lower, but if perfusion is maintained, no intervention is required

For information only, Premature : Heart rate (beats/min): 120-170*; Blood pressure (mm Hg): 55-75/35-45; Respiratory rate (breaths/min): 40-70

Reference ranges for magnesium are presented in [Table 16-2](#) and for potassium in [Table 16-3](#) (adapted from [Hay et al 2018](#)).

Table 16-2 Reference ranges for magnesium (mg/dL) by age range (male-female)

| Age | Male | Female |
|------------|---------|---------|
| 0-7 days | 1.2-1.6 | 1.2-1.6 |
| >7-30 days | 1.6-2.4 | 1.6-2.4 |
| >1 mo-2 y | 1.6-2.6 | 1.6-2.6 |
| >2-6 y | 1.5-2.4 | 1.5-2.4 |
| >6-10 y | 1.6-2.3 | 1.6-2.3 |
| >10-14 y | 1.6-2.2 | 1.6-2.2 |
| >14 y | 1.5-2.3 | 1.5-2.3 |

Table 16-3 Reference ranges for potassium (mmol/L) by age range (male-female)

| Age | Male | Female |
|------------|---------|---------|
| 0-7 days | 3.7-5.9 | 3.7-5.9 |
| >7 d-3 mo | 4.1-5.3 | 4.1-5.3 |
| >3 mo-18 y | 3.4-4.7 | 3.4-4.7 |
| >18 y | 3.5-5.0 | 3.5-5.0 |

Reference curves from WHO for head circumference are presented in [Figure 16-1](#) and [Figure 16-2](#) for males, and in [Figure 16-3](#) and [Figure 16-4](#) for females (https://www.who.int/childgrowth/standards/hc_for_age/en/).

[figure not shown]
Figure 16-1 Reference ranges for head circumference in males (0-13 weeks)

[figure not shown]
Figure 16-2 Reference ranges for head circumference in males (0-2 years)

[figure not shown]
[figure not shown]
Figure 16-3 Reference ranges for head circumference in females (0-13 weeks)

Figure 16-4 Reference ranges for head circumference in females (0-2 years)

16.2 Appendix 2: Liver event and Laboratory trigger Definitions and Follow-up Requirements

Table 16-4 Follow up requirements for liver events and laboratory triggers

| ALT | TBL | Liver symptoms | Action |
|--|---|----------------|--|
| ALT increase without bilirubin increase | | | |
| If normal at baseline: Normal ALT > 3 x ULN | | None | No change to study treatment • Measure ALT, AST, ALP*, GGT*, TBIL, INR*, albumin*, CK*, and GLDH* in 48-72 hours. • Follow-up for symptoms. |
| If elevated at baseline: ALT > 2 x baseline or > 200 U/L (whichever occurs first) | For patients with Gilbert's syndrome: No change in baseline TBL | None | No change to study treatment • Measure ALT, AST, ALP*, GGT*, TBIL, INR*, albumin*, CK*, and GLDH* in 48-72 hours. • Follow-up for symptoms. |
| If normal at baseline: Normal ALT > 5 x ULN for more than two weeks | | None | Interrupt study drug • Measure ALT, AST, ALP*, GGT*, TBIL, INR*, albumin*, CK*, and GLDH* in 48-72 hours. • Follow-up for symptoms. • Initiate close monitoring and workup for competing etiologies. • Study drug can be restarted only if another etiology is identified and liver enzymes return to baseline. |
| If elevated at baseline: ALT > 3 x baseline or > 300 U/L (whichever occurs first) for more than two weeks | For patients with Gilbert's syndrome: No change in baseline TBL. | None | Interrupt study drug • Measure ALT, AST, ALP*, GGT*, TBIL, INR*, albumin*, CK*, and GLDH* in 48-72 hours. • Follow-up for symptoms. • Initiate close monitoring and workup for competing etiologies. • Study drug can be restarted only if another etiology is identified and liver enzymes return to baseline. |
| If normal at baseline: Normal ALT > 8 x ULN | • | None | Interrupt study drug • Measure ALT, AST, ALP*, GGT*, TBIL, INR*, albumin*, CK*, and GLDH* in 48-72 hours. • Follow-up for symptoms. • Initiate close monitoring and workup for competing etiologies. • Study drug can be restarted only if another etiology is identified and liver enzymes return to baseline. |
| ALT increase with bilirubin increase: | | | |

| ALT | TBL | Liver symptoms | Action |
|--|---|---|--|
| If normal at baseline: ALT > 3 x ULN | TBL > 2 x ULN (or INR > 1.5) | None | Interrupt study drug • Measure ALT, AST, ALP*, GGT*, TBIL, INR*, albumin*, CK*, and GLDH* in 48-72 hours. • Follow-up for symptoms. • Initiate close monitoring and workup for competing etiologies. • Study drug can be restarted only if another etiology is identified and liver enzymes return to baseline. |
| If elevated at baseline: ALT > 2 x baseline or > 200 U/L (whichever occurs first) | For patients with Gilbert's syndrome: Doubling of direct bilirubin | None | Interrupt study drug • Measure ALT, AST, ALP*, GGT*, TBIL, INR*, albumin*, CK*, and GLDH* in 48-72 hours. • Follow-up for symptoms. • Initiate close monitoring and workup for competing etiologies. • Study drug can be restarted only if another etiology is identified and liver enzymes return to baseline. |
| If normal at baseline: ALT > 3 x ULN | Normal elevated | Severe fatigue, nausea, vomiting, right upper quadrant pain | Interrupt study drug • Measure ALT, AST, ALP*, GGT*, TBIL, INR*, albumin*, CK*, and GLDH* in 48-72 hours. • Follow-up for symptoms. • Initiate close monitoring and workup for competing etiologies. • Study drug can be restarted only if another etiology is identified and liver enzymes return to baseline. |
| If elevated at baseline: ALT > 2 x baseline or > 200 U/L (whichever occurs first) | Normal elevated | Severe fatigue, nausea, vomiting, right upper quadrant pain | Interrupt study drug • Measure ALT, AST, ALP*, GGT*, TBIL, INR*, albumin*, CK*, and GLDH* in 48-72 hours. • Follow-up for symptoms. • Initiate close monitoring and workup for competing etiologies. • Study drug can be restarted only if another etiology is identified and liver enzymes return to baseline. |

* If clinically indicated and within blood draw limitations

